5.0 STUDY METHODS

5.1 Study Design

This is a pilot pragmatic, non-inferiority, open label randomized controlled trial (RCT) in outpatients with iron deficiency anemia to evaluate the effectiveness of oral ferrous sulfate 300mg (60mg elemental iron) once daily versus every other day to improve hemoglobin at 12 weeks post-initiation. Patients will be randomized according to a computer-generated allocation sequence to receive either once daily dosing or every other day dosing. Randomization will be stratified by centre and baseline hemoglobin (hemoglobin \geq 100 g/L OR $<$ 100 g/L). Following randomization, patients will receive oral iron tablets for a period of 12 weeks, with clinical and subjective data collection occurring 1, 4, 8 and 12 weeks following the commencement of oral iron. The study will aim to recruit 52 patients in total, randomizing 26 patients to each study arm. This sample size includes an anticipated 30% drop out rate (see section 8.1).

5.2 Study Population

We propose broad eligibility criteria to increase the generalizability and feasibility of the proposed trial. The exclusion criteria are predominantly conditions where oral iron has already been shown to be ineffective. There are no exclusions based on sex, race or ethnicity in this trial.

5.2.1 Inclusion Criteria

- Age \geq 16 years;
- Outpatients with iron deficiency anemia defined as hemoglobin less than 120 g/L in women or less than 130 g/L in men; AND ferritin less than 30 mcg/L.

5.2.2 Exclusion Criteria

- Pregnancy
- Currently breastfeeding
- Known history of inflammatory bowel disease
- Known history of celiac disease
- Known history of thalassemia or thalassemia trait
- Known inherited bleeding disorder

- Known intolerance or lack of response to oral ferrous gluconate, sulfate or fumarate in the last 12 weeks
- Multivitamin and mineral supplements (35 mg or more of elemental iron per day) in the 2 weeks prior to randomization
- Allergy to oral iron
- Allergy to any of the following medicinal and non-medicinal ingredients in ferrous sulfate: ferrous sulphate, calcium citrate, crospovidone, FD&C Red #40-Aluminum lake, FD&C Yellow #6-Aluminum Lake, magnesium stearate, microcrystalline cellulose, polyethylene glycol, polyvinyl alcohol, purified water, talc titanium dioxide
- Allergy to any of the following medicinal and non-medicinal ingredients in vitamin C: Ascorbic acid, Colloidal silicon dioxide, croscarmellose sodium, magnesium stearate, microcrystalline cellulose and stearic acid
- Intravenous iron therapy in the past 12 weeks
- On new anticoagulant therapy initiated in the past 6 months (e.g. warfarin, apixaban, dabigatran, edoxaban, rivaroxaban)
- Surgery planned in upcoming 12 weeks
- Chemotherapy planned in upcoming 12 weeks
- Blood donation planned in upcoming 12 weeks
- Previously enrolled in the study
- Creatinine clearance less than 30 mL/min
- Hemoglobin less than 80 g/L with active bleeding (defined as WHO grade 2 bleeding or higher in the past week)

5.3 Study Activities

5.3.1 Patient recruitment, consent, screening and enrolment

Patients meeting inclusion criteria will be identified through referring clinician offices (hematology and primary care physicians). Initial contact about the study will be made by a health care provider from the patient's clinical team. Study personnel will approach the MRP for permission to approach the patient or ask that they introduce the study to the patient. With permission to enter the patient's circle of care, the research coordinator will then approach potentially eligible patients. The research coordinator will introduce the trial, confirm eligibility and conduct the informed consent discussion. The study personnel will screen patients for exclusion criteria by asking about the patient's medical history and reviewing their bloodwork that will be taken as a standard of care when visiting the MRP. Patients interested in participating and meeting both inclusion and no exclusion criteria will be given an Informed Consent Form. This discussion will include the rationale for the study, the anticipated risks and benefits of participation, and their rights as a study participant (including withdrawal at any time). Capable participants will be offered an opportunity to ask questions and consult with their family and/or their physician before enrollment. If the patient is deemed incapable of providing informed consent for the study, study personnel will approach the patient's physician to determine if it is safe to delay treatment while a substitute decision maker is identified and approached. As the initiation of oral iron is not urgent, there will be enough time to assess the patient for inclusion in the study before initiating treatment. The subject will be invited to participate and must provide informed consent prior to any study related procedures. One signed copy of the informed consent will be placed in the participant's medical record, another copy given to the participant and the original kept in the study file with the research coordinator. Once the subject is enrolled, his/her family physician will be informed about

his/her participation in the study. If the participant does not wish to participate, the reason for declining will be documented. Patients will be identified by initials only on the screening log.

Another potential recruitment site will be through Canadian Blood Services. Blood donors that have been deferred due to low hemoglobin levels (within the local Toronto area close to hospital study sites) will be provided with a letter (see Supporting Documents) which explains that the donor was deferred and for the donor to see visit their family physician for further investigation. In addition, a letter to the family physician will explain key points about the study purpose, rationale, procedures and detailed information about the DEODO trial. If the patient is interested in participating in the study, after visiting their family physician, the family physician can refer the patient to one of the study sites. The letter contains contact information for the Principal Investigator and Research Coordinator if the patient or their family physician has any questions. It is also acceptable for the patient to contact the study site directly in which case permission from the MRP is not required. Once the patient is referred to or has contacted a study site, then consent will occur as outlined in the previous paragraph.

Once the patient has consented, bloodwork will be performed at the participating institution's laboratory or at a local lab, if it has not been performed in the past 2 weeks. Eligibility of the patient will be determined. If the eligibility is confirmed, then the patient will be enrolled (assigned a study ID) and randomized. Any additional bloodwork required within the pre-specified time frame (see 5.4.1.2) can be drawn or added on to the bloodwork already completed.

All sites will obtain Research Ethics Board (REB) approval of the protocol and the informed consent form. A recruitment log of eligible and ineligible patients as well as reasons for non-consent will be kept at each participating centre. We anticipate that this study will take 2 years to complete.

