5.4.1.2 Baseline Laboratory Assessment

- Hemoglobin, reticulocyte count, ferritin, serum iron, TSAT, C reactive protein within 2 weeks of randomization (and at least 2 weeks off any oral iron supplementation)
- Creatinine within 3 months of randomization
- Screening bloodwork can be used for the baseline laboratory assessment

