5.4.2 Follow-up Visits and Assessments

5.4.2.1 Week 1

Participants will be contacted by telephone or email for the following assessment at Day 7 ± 3 days

- Adherence as determined by patient diary (supporting documents)
- Side effect questionnaire (supporting documents)

5.4.2.2 Week 4

Participants will be contacted by telephone or email at Day 28 ± 7 days for the following assessment

- Adherence as determined by patient diary
- Side effect questionnaire
- FACIT-fatigue scale questionnaire
- Medication history (to confirm if any new or discontinued medications)
- Reminder to do laboratory tests (at the local site or local lab) for CBC, reticulocyte count

At the week 4 assessment, if the participant has a drop in hemoglobin of more than 10 g/L from baseline, then the patient will be referred back to the most responsible physician for management and escalation of therapy. If the patient receives escalation of therapy (need for alternative oral iron therapy including if a participant in the every other day group escalates to daily iron, need for intravenous iron, need for transfusion, visit to emergency department related to anemia), the participant will no longer complete any further study assessments and the most responsible physician will be notified. The reason for the drop in hemoglobin will be classified as: ongoing bleeding; non-compliance (defined as less than 50% of pills); other reason; or no clear reason.

5.4.2.3 Week 8

Participants will be contacted by telephone or email at Day 56 ± 7 days for the following assessment

- Adherence as determined by patient diary
- Side effect questionnaire
- FACIT-fatigue scale questionnaire
- Medication history (to confirm if any new or discontinued medications)

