5.4.2.4 Week 12 Final Study Visit

Participants will be assessed in person/remotely (telephone/zoom/OTN) at Day 84 ± 7 days for the following assessment

- Adherence as determined by patient diary and pill count
- Side effect questionnaire
- FACIT-fatigue scale questionnaire
- Medication history (to confirm if any new or discontinued medications)
- Laboratory tests: CBC, reticulocyte count, ferritin, serum iron and TSAT
- Need for escalation in therapy: Y/N
 - Increase in oral iron regimen from every other day to daily
 - Intravenous iron
 - Transfusion
 - Visit to emergency department related to anemia

5.4.2.5 Week 13

Participants will be contacted by telephone or email at $7 \text{ days} \pm 3$ days after the Week 12 final study visit for assessment of adverse and serious adverse events.

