7.2 Secondary outcome assessments

Feasibility

1. Proportion of eligible patients consenting to participate

$$\frac{\# \text{ meeting eligibility criteria} - \# \text{ in whom consent not obtained}}{\# \text{ meeting eligibility criteria}}$$

2. Proportion of consenting patients receiving the allocated treatment

consenting to treatment - # not administered allocated treatment
consenting to treatment

3. Proportion of treated patients completing 4 week and 12 week laboratory tests

completing 100% of 4 week and 12 week lab tests
consenting to treatment

4. Proportion of treated patients completing 4 week, 8 week and 12 week side effect questionnaire

completing 100% of 4 week, 8 week and 12 week side effect questionnaire
consenting to treatment

5. Proportion of treated patients completing 4 week, 8 week and 12 week FACIT-fatigue scale

completing 100% of 4 week, 8 week and 12 FACIT-fatigue scale
consenting to treatment

6. Proportion of treatment doses taken as per protocol based on pill count

$$\frac{\text{total # of doses} - \text{# of missed doses}}{\text{total # of doses}}$$

7. Proportion of treated patients taking at least 90% of their prescribed doses

$$\frac{\text{# of patients taking at least 90% of prescribed doses}}{\text{total # of treated patients}}$$

8. Proportion of treated patients requiring a step down in therapy

$$\frac{\text{# of patients requiring step down in therapy}}{\text{total # of treated patients}}$$

Clinical/Safety

9. Hemoglobin increment at 4 and 12 weeks is defined as the 4 or 12 week hemoglobin value minus the baseline hemoglobin value

10. Proportion with complete hemoglobin response defined as hemoglobin greater than or equal to 120 g/L in women; and 130 g/L in men at 4 weeks and 12 weeks

11. Change in reticulocyte count at 4 and 12 weeks defined as the 4 or 12 week reticulocyte count minus the baseline reticulocyte count

12. Change in ferritin, serum iron and TSAT at 12 weeks defined as the value at 12 weeks minus the baseline value

13. Quality of life (FACIT-fatigue scale) at 4, 8 and 12 weeks

14. Proportion with side effects and type of side effects at 4, 8 and 12 weeks as determined by the oral iron side effect questionnaire
15. Proportion of patients who stop taking oral iron due to side effects at 4 and 12 weeks

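### A patient's baseline and follow-up blood tests need not come from the same laboratory, so within-patient changes in hemoglobin and iron indices may carry avoidable between-laboratory error

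*Combined protocol and SAP*

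**What the plan says.** **Baseline.** Under 5.3.1, study staff screen by "reviewing their bloodwork that will be taken as a standard of care when visiting the MRP". After consent, blood is drawn at the institution's "laboratory or at a local lab, if it has not been performed in the past 2 weeks". Analytes still missing "can be drawn or added on to the bloodwork already completed", so even one baseline panel can come from two laboratories. Section 5.4.1.2 adds: "Screening bloodwork can be used for the baseline laboratory assessment".

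**Week 4 (5.4.2.2).** "Reminder to do laboratory tests (at the local site or local lab) for CBC, reticulocyte count".

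**Week 12 (5.4.2.4).** "Laboratory tests: CBC, reticulocyte count, ferritin, serum iron and TSAT", with no laboratory named. The visit itself may be remote: "Participants will be assessed in person/remotely (telephone/zoom/OTN) at Day 84".

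**Outcomes (7.2).** Item 9: "Hemoglobin increment at 4 and 12 weeks is defined as the 4 or 12 week hemoglobin value minus the baseline hemoglobin value". Items 11 and 12 define the changes in reticulocytes, ferritin, serum iron and TSAT in the same way. Item 17 is a fall in hemoglobin of at least 10 g/L, which 3.4 measures from baseline.

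The baseline, visit, outcome and analysis sections and the Appendix C schedule contain no request for one laboratory per patient, no central laboratory, and no analysis that allows for a change of laboratory.

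**The concern.** A laboratory's calibration offset cancels from a within-patient change only if both values come from that laboratory. Recruitment through primary care offices and deferred blood donors (5.3.1) makes a community baseline followed by a hospital test, or the reverse, an ordinary path.

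The increment SD is what is mainly at stake. Footnote B to Table 2 says that no such SD was available and builds one from assumed correlations, and 8.1 lists better numbers for the definitive trial among the pilot's aims. Table 2 is steep in this input: at a true difference of 0 and 90% power it asks for 36, 80 or 140 evaluable patients at an SD of 5, 7.5 or 10 g/L. An offset could also help to create or conceal a 10 g/L fall, both in item 17 and in the week 4 check in 5.4.2.2.

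**Working it through.** **1. The plan's own figure.** Inputs from 8.1 and Table 2: margin 5 g/L, one-sided 95% interval (footnote C), true difference 0, SD 5, 90% power, 30% dropout, 1:1 allocation. The normal approximation gives n per arm = 2 × (1.645 + 1.282)² × 5² / 5² = 17.1, so 18 per arm and 36 in total. Then 36 / 0.70 = 51.4, so 52. A noncentral-t calculation reproduces the unadjusted total in all 12 rows of Table 2.

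**2. Model for a laboratory switch.** Let s be the SD of laboratory offsets for one measurement and f the share of patients whose two values come from different laboratories. Take offsets as independent with mean zero, and as cancelling exactly when the laboratory is the same. Then

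SD′ = √(SD² + 2·s²·f), and required N is multiplied by about (SD′/SD)².

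Neither s nor f is in the documents; both are assumptions, shown over a range.

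**3. From the plan's SD of 7.1** (footnote B: pre and post SDs of 10, correlation 0.75; 7.1² = 50.41):

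| s (g/L) | half switch: SD′ | N | all switch: SD′ | N |
|---|---|---|---|---|
| 1 | √51.41 = 7.17 | +2% | √52.41 = 7.24 | +4% |
| 2 | √54.41 = 7.38 | +8% | √58.41 = 7.64 | +16% |
| 3 | √59.41 = 7.71 | +18% | √68.41 = 8.27 | +36% |

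**4. From the SDs in Table 2,** half switching, evaluable N for 90% power (noncentral t):

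| Base SD | no switching | s = 1 | s = 2 | s = 3 |
|---|---|---|---|---|
| 5 | 36 | 38 | 42 | 50 |
| 7.5 | 80 | 80 | 84 | 92 |
| 10 | 140 | 140 | 144 | 152 |

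At a base SD of 5 with 36 evaluable patients, power falls from 90% to 89%, 86% or 81%.

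**5. Against the 10 g/L threshold.** In a patient who switches, the difference of two offsets has SD √2·s, which is 1.4, 2.8 or 4.2 g/L for s = 1, 2 or 3. That can move a patient who is already near the threshold across it. How often this would happen cannot be derived from the documents.

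**The case against.** **The primary outcome is unaffected and the arms are treated alike.** This stands. The primary outcome is time to enroll 52 patients. Both arms follow the same laboratory rules and randomization is stratified by centre. A reader might infer a biased comparison, but the documents give no reason to expect switching to differ by arm.

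**The larger SD may be the right one.** If the definitive trial lets patients use any laboratory, an SD that includes this variation is the correct planning value. This stands in part. The documents do not say how the definitive trial will handle laboratories. That is a reason to record the laboratory, so that both SDs can be reported.

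**The effect is small beside sampling error.** An SD estimated from 36 completers (34 degrees of freedom) has a 95% interval of about 0.81 to 1.31 times its value, so the planned N could range from 0.65 to 1.72 times. All the increases in step 3 lie inside that range. This limits the importance of the point, but sampling error cannot be removed without more patients, whereas this component can.

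**The local laboratory option was deliberate.** The summary of changes gives COVID-19 safety as the reason. This stands, and the fix keeps the option. A rigid rule could also reduce completion of the week 4 and week 12 tests, which is itself a feasibility outcome (item 3).

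**Week 12 rests on silence.** This stands. Only baseline and week 4 expressly allow a local laboratory. For week 12 there is only the absence of a named laboratory and the remote visit option.

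**The laboratory may be recoverable.** Laboratory reports are reviewed as needed under 14.3, and the case report forms are not in the documents, so it cannot be said that a laboratory field is missing.

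**Conclusion.** The point holds as a modest, cheaply avoided loss of precision. The plan permits a change of laboratory between a patient's baseline and week 4 values and does not exclude one at week 12, while the secondary laboratory outcomes are differences from baseline. With an assumed between-laboratory SD of 1 to 3 g/L and a base SD of 7.1, the required N for the definitive trial rises by 2% to 18% if half of patients switch and by 4% to 36% if all do. It rises by less if switching is rarer or the underlying SD is larger.

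Three further readings are tempting but unsupported:

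- **CRP subgroup.** Section 8.2 refers only to the normal range, without saying whose. CRP is scheduled only before enrolment, so it is not a within-patient change, and a same-laboratory rule would not alter it.
- **A bound on ferritin error.** Changes in ferritin, iron and TSAT are exposed in the same way, but the entry limit of 30 mcg/L does not cap the week 12 value, so no maximum error follows from it.
- **Treatment escalation caused by a laboratory offset.** A fall of more than 10 g/L at week 4 leads to referral to the responsible physician, not automatically to escalation.

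**What to change.** In 5.4.1.2, 5.4.2.2 and 5.4.2.4, ask that the week 4 and week 12 tests be done, where practical, at the laboratory that gave the patient's baseline value. State that local laboratories remain allowed and that a test done elsewhere is better than a missed test. Record the laboratory for each draw. In 8.2, add that the mean and SD of the hemoglobin increment will also be reported in patients with one laboratory throughout. That subset will be smaller than the 36 completers sought, so it serves to describe the SD for planning and not as a test.

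The cost is a sentence in each section and one recorded item per draw, with no extra blood samples. Patients have slightly less choice of location, and there may be a small effect on test completion, which the where-practical wording is meant to limit. The record would also show how often patients switch, which is useful for designing the definitive trial.

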5.3.2 Randomization and stratification

Randomization allocation will be performed by Clinical Trial Services at Sunnybrook Health Sciences Centre using a computer generated allocation sequence. The randomization code will be generated in random blocks of 4 to 6, stratified by centre, and hemoglobin at time of randomization (hemoglobin greater or equal to 100 g/L or less than 100 g/L). Randomization will be provided to the sites in opaque numbered envelopes. The study is an open-label study. The research coordinator/assistant will enroll participants for this study.

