5.3.3.2 Acquisition and Formulation

Once randomization has occurred, a prescription for the dosing regimen will be given to the patient to bring to pharmacy at the local site. Patients opting for virtual clinic visits will have their prescription filled by the study coordinator, and the pills couriered to their address on file. Patients will also have the

option to pick-up their prescription from the study site (curbside pick-up). There will be two randomization groups, one for hemoglobin ≥ 100 g/L (Mild IDA) and one for hemoglobin < 100 g/L (Moderate IDA).

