12.0 STUDY ADMINISTRATION

The coordinating site will be Sunnybrook Health Sciences Centre. The site research coordinators will be responsible for trial coordination, site training, site start-up/activation, document management, supply management, database development, data management and statistical analysis. Study data and patient surveys will be entered and maintained on a secure password protected database developed using REDCap (www.projectredcap.org) and will be accessible via the Internet for data entry purposes.

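### Printed small block sizes and site envelopes with no stated custodian, in an open-label trial, make about 3 of 52 allocations certain in advance and leave early opening unguarded

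*Combined protocol and SAP*

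**What the plan says.** Section 5.3.2 (Randomization and stratification) puts the following together:

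- Sequence: "The randomization code will be generated in random blocks of 4 to 6, stratified by centre, and hemoglobin at time of randomization", with hemoglobin split at 100 g/L. Clinical Trial Services at the coordinating hospital generates it by computer.
- Delivery: "Randomization will be provided to the sites in opaque numbered envelopes".
- Masking: "The study is an open-label study".
- Enrolment: "The research coordinator/assistant will enroll participants for this study".

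Section 5.3.1 gives the coordinator the steps before that as well: "The research coordinator will introduce the trial, confirm eligibility and conduct the informed consent discussion". Section 12.1 repeats that coordinators at each site screen, consent and enrol.

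Coordinators also learn past assignments. Under section 5.3.3.2, patients with virtual visits "have their prescription filled by the study coordinator". Section 5.3.5.3 issues a diary specific to the regimen, and section 5.4.4 has the coordinator or assistant discuss adherence with the patient directly.

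The protocol does not say who keeps or opens the envelopes, whether they are sealed or opened in order, whether openings are logged, or that block sizes are withheld from sites. Sites hold the protocol, since section 5.3.1 requires each to obtain ethics approval of it.

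**The concern.** In an open-label trial the sequence stays unpredictable only if the people who enrol cannot work out or see the next assignment. Here they know the earlier ones, can read the block sizes, and work at a site where the coming assignments sit in envelopes without stated safeguards.

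The plan leaves room for such knowledge to matter. Section 5.3.1 says that starting oral iron is not urgent, so enrolment can be delayed without clinical pressure. Section 5.3.4 expects about 30% of patients may not tolerate oral iron. Section 5.3.1 has study personnel ask about medical history at screening, so they may form a view of who would struggle with daily dosing.

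What is exposed is the set of secondary between-arm comparisons: adherence, step-down, side effects, stopping for side effects and hemoglobin increment. Section 8.2 says the pilot will inform the design of the definitive trial, and section 8.1 sets a 5 g/L non-inferiority margin for that trial's hemoglobin comparison. The primary outcome, time to enroll 52 patients, is not a comparison between arms.

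**Working it through.** **Inputs**

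- Total 52, with 26 per arm (section 5.1). This reproduces from Table 2 (SD 5, margin 5, one-sided 5%, 90% power): 2 × (1.645 + 1.282)² × 5²/5² = 17.1, so 18 per arm and 36 in total; 36/0.70 = 51.4, rounded up to 52.
- Two centres (section 2.2) and two hemoglobin groups give 2 × 2 = 4 strata. If evenly filled, 52/4 = 13 patients each. Even filling is an assumption, so uneven splits were also run.
- Blocks of 4 to 6 (section 5.3.2). With 1:1 allocation a block of 5 cannot balance, so the sizes are taken as 4 and 6. The mix is not stated and is assumed equal.

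The plan gives no predictability figure to reproduce.

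**Step 1: guessing without knowing the block sizes.** The guesser picks the arm that is behind in the stratum and tosses a coin when the arms are level. For a complete block of 2b patients the expected number correct is b + 2^(2b−1)/C(2b,b) − 1/2.

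- Block of 4: 2 + 8/6 − 0.5 = 2.833; 2.833/4 = 70.8%.
- Block of 6: 3 + 32/20 − 0.5 = 4.1; 4.1/6 = 68.3%.
- Equal mix: (2.833 + 4.1)/10 = 69.3%.

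Incomplete last blocks lower this. Simulated over 52 patients (20,000 runs per split):

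| Patients per stratum | Correct guesses |
|---|---|
| 13/13/13/13 | 67.3% (5th to 95th percentile 63.5% to 70.2%) |
| 20/16/10/6 | 68.2% |
| 30/14/6/2 | 68.0% |
| 36/10/4/2 | 67.9% |
| 26/26 | 68.7% |

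At 13 per stratum, all blocks of 4 give 69.2% and all blocks of 6 give 66.9%. The 26/26 row covers the synopsis, which lists only the hemoglobin strata and omits centre.

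**Step 2: guessing with the sizes known.** A Bayes-optimal guesser who knows the sizes are 4 and 6 gets 67.3% at 13 per stratum (4,000 runs), the same as in step 1. Printing the sizes adds nothing to the average.

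**Step 3: what the printed sizes do add.** If the first three patients in a stratum all receive the same arm, the block cannot be a 4, which holds only two of each. It must be a 6, so the next three assignments are known. Counting every such case, 6.0% of assignments are certain at 13 per stratum (5.3% to 6.1% over the splits). 0.06 × 52 = 3.1, or about 3 patients. Someone who does not know the sizes cannot be certain of these.

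**Step 4: weaker guessers.** Ignoring the hemoglobin stratum gives 62.5% correct. Guessing the opposite of the last assignment in the stratum gives 59.6%.

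**Step 5: other block schemes.** With the step 1 strategy, 13 per stratum and sizes equally likely, 4/6/8 gives 66.0% and 8/10/12 gives 62.8%. Unrestricted randomization gives 50%.

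**The case against.** A reader might infer that envelopes and printed sizes are why a coordinator could guess two-thirds of assignments, and that full concealment would bring this to 50%. The calculation does not support that. The same 4/6 sequence, perfectly concealed and centrally released, would still be guessed at about 67% in an open-label trial. The 50% figure belongs to unrestricted randomization only.

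A reader might also infer that the enrolling coordinator holds the next envelope. Section 5.3.2 says only that envelopes go to the sites. The gap is that custody is unspecified.

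Other points on the plan's side have weight:

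- The 67% is a ceiling for someone who tracks every assignment by stratum. The summary of changes for version 3 mentions coordinator turnover, which makes unbroken tracking by one person less likely.
- Section 5.3.1 places consent and confirmed eligibility before randomization and requires logs of eligible and ineligible patients with reasons for non-consent, so selective enrolment would leave some trace. These logs do not prevent delayed approach or early opening of an envelope.
- The core entry criteria are laboratory values, and known intolerance to oral iron in the last 12 weeks is an exclusion (section 5.2.2). This narrows the scope for steering but does not remove it.
- The between-arm comparisons are secondary in a pilot, and no size of bias can be derived from the documents.

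These points limit the weight of the concern. They do not explain why the sizes need to be in the sites' protocol or why envelope safeguards are unstated.

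**Conclusion.** The point holds as an avoidable weakness in concealment that should be corrected. Printing the sizes makes about 6% of assignments (about 3 of 52) certain to someone who knows them and tracks the stratum. Site envelopes with no stated custodian, order of opening or log leave early or out-of-order opening unguarded. The average guess rate of about 67% (67% to 69% over the splits tried, about 60% to 62% for less careful guessers) is a separate property of small balanced blocks plus open-label knowledge.

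The figures rest on sizes 4 and 6 being equally likely and on the assumed stratum sizes. They measure opportunity and do not show that selection occurred or that any comparison is biased. The exposure lies in the secondary comparisons carried into the definitive trial; the primary outcome is little affected.

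**What to change.** 1. Take the block sizes out of section 5.3.2 and put them in a restricted randomization document. Choose new, more varied sizes and do not disclose them to sites. Withholding them deals with the certain assignments. Changing them lowers the average only modestly: about 66% with 4/6/8 and about 63% with 8/10/12. The cost is a slightly higher chance of imbalance within small strata, because the largest possible gap between arms in a stratum is half the largest block: 3 now, 4 with 8s and 6 with 12s.
2. Replace site envelopes with release of each allocation by Clinical Trial Services after consent, eligibility and stratum are recorded. This removes early and out-of-order opening and follows the order already in section 5.3.1. Clinical Trial Services already generates the sequence, and study data are already "entered and maintained on a secure password protected database developed using REDCap" (section 12.0). The documents describe that database for data entry only, so modest set-up is needed, and sites need access at randomization.
3. In the same amendment, reconcile the synopsis, which omits centre as a stratification factor, with sections 5.1 and 5.3.2.

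The wording changes need an amendment approved by each site's ethics board.
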